#### **5.4 Pain Management**

The decision to administer pain medication therapy in the pre- and post-operative/follow-up setting is at the discretion of the Investigator/Institution taking into consideration the subject's ability to safely take pain medication therapy.

It is recommended that a multi-modal pain regimen be considered which would include, but not be limited to: ice, elevation, local & regional anesthesia, NSAIDs, acetaminophen, neuro-modulation drugs and narcotics.

The decision of which pain medications to use (if any) is left to the discretion of the Investigator. Pain medications taken for pain management during the pre- and post-operative/follow-up period will be recorded.

## 6.0 IDENTITY OF STUDY DEVICES

### The devices utilized for the study include:

Mini-Incision™ Precision Instrument Set

Lapiplasty® Mini-Incision™ System

The TMC Plating System is intended for use in stabilization of fresh fractures, revision procedures, joint fusion and reconstruction of small bones of the feet. The system can be used in both adult and pediatric patients aged >12 years.

All medical devices used during this study are cleared for commercial distribution and are to be used in accordance with approved product labeling.

### Device Description

The Lapiplasty® Mini-Incision™ Precision Instrument Set includes the SpeedSeeker™ Instrument, the Mini-Incision™ Positioner, the Mini-Incision™ Cut Guide and the Plate Holder. These are reusable instruments and not unique to each patient. The actual components in the instrument pack may vary by site.

[figure not shown]
The Lapiplasty® Mini-Incision™ includes the Mini-Incision™ Plate and the PlantarPower™ Plate and locking screws. The PlantarPower™ Plate is uniquely contoured to span plantarly across the tension-side of the 1st TMT joint, while providing easy access to each locking screw without the need for extensive retraction of the mini dorsal incision. (See Figure 1)

**Figure 1**

### Mini-Incision™ Precision Instrument Set

## Lapiplasty® | Mini-Incision™ System

### 6.1 Product Accountability

Commercially available devices will be utilized for the study subjects; therefore, product accountability and reconciliation records will not be required. Devices will not be provided by the sponsor. Study devices and instruments that are used during each procedure will be documented on the eCRFs as listed in Visit 2.

## 7.0 SUBJECT VISITS

Details for specific subject visit activities are found below and reflect the Schedule of Assessments table.

### 7.1 Visit 1 – Baseline

Subjects will be screened for study participation during the baseline visit. The procedures required for the baseline visit may be conducted during more than one visit. Some baseline procedures may have been completed as patient standard of care (including radiographic imaging) and therefore may be completed prior to informed consent and do not need to be repeated after consent.

The following procedures must be conducted within 90 days prior to the index procedure.

- Informed Consent
- Demographics [including foot size (length and width) of operative foot and work status/work classification]
- Relevant Medical and Surgical History, including any previous history of foot surgery and any pre-planned surgical foot procedures
- Targeted Physical Exam
- Height / Weight (including BMI calculation)
- Blood Collection – (fasting plasma glucose or HbA1c – only required if patient has current clinical diabetes diagnosis)
- 4-Point Monofilament Test (only required if patient has current clinical diabetes diagnosis or if suspicion of peripheral neuropathy based on medical history)
- Clinical Examination of Operative Foot
- Foot Measurements
- Range of Motion
- Radiographic Imaging
  - Weight-bearing AP, lateral and axial views of operative foot
- Radiographic Measurements
  - Note: For the purposes of determining IMA, HVA and MAA for patient eligibility, measurements will be made according to institutional SOC. For the purposes of all data analysis, measurements by the central radiologist will be utilized. If there are minor differences in baseline IMA, HVA and MAA measurements made by the central radiologist, the measurements of the PI/site will remain acceptable for determining patient eligibility.
- VAS Pain Scale
- QOL Measurements
- Digital photograph of operative foot, preferred but not required
- Medications Review
- Pregnancy Test (if female of childbearing potential)
  - Must be within 7 days of index procedure or may be completed on day of index procedure
- Inclusion/Exclusion Criteria

## 7.2 Visit 2 –Index Procedure

The following must be conducted:

- Exclusion Criteria (confirm patient has abstained from nicotine use prior to anesthesia)
- Medical History [if relevant medical history (e.g., related to bone quality or patient condition that does not exclude them from participation in study) is identified during index procedure]
- Foot Measurements
- Index Procedure
  - Start and stop time of tourniquet placement
  - Time of first incision and placement of final plate screw
  - Length of incision at start of procedure
  - Extension of incision and location of extension (proximal, distal or both), as applicable
  - Completion of lateral release
  - Use of SpeedSeeker™ device (or fulcrum and joint seeker)
  - Total length of time of use of Mini-Incision™ Positioner
  - Use of Mini-Incision™ Cut guide
  - Joint morphology of articular surface (uni-facet, bi-facet, or tri-facet), if feasible
  - Use of Compressor device
  - Use of Mini-Incision™ System
  - Use of Transverse Screw and location of screw placement, if applicable
  - Use of Interfrag Screw at TMT joint, if applicable
  - Use of additional plate screws (Long Screw Pack, FastPitch™ Screw Pack, other), if applicable
  - Use of Headless Screw for Akin procedure, if applicable
  - Length of incision after suturing complete
    - If incision required extension beyond >4.0 cm to complete Index Procedure, the subject will be treated as a screen failure.
- Digital photograph of operative foot, post-incision, not required
- Post-op surgical dressing/protection utilized
- Concomitant Procedures performed
- Deviations/Delays to Normal Operative Plan
- Medications Review (Pre-operative and Post-operative)
- Adverse Events Assessment, including Intra-Operative Procedural Complications
- Post-op Care instructions review
  - Post-op mobility assistance device utilized
- Post-op Weight-Bearing protocol instructions review

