### **Secondary:**

1. Change in radiographic angular/positional alignment before and after the Lapiplasty® Procedure [Time Frame: pre-operatively, 6 weeks, 4 months, 6 months, 12 months, and 24 months, post-Lapiplasty® Procedure].
2. Evaluate clinical/radiographic healing (union vs non-union). Non-union defined as lucency at TMT joint, hardware failure and/or loss of correction (recurrence), plus clinical pain at first TMT joint at 12 months post- Lapiplasty® Procedure.
3. Clinical complications through 24-month follow-up visit due to the Lapiplasty® System Implants, the Lapiplasty® Procedure, the post-operative weight-bearing protocol or health conditions that could affect other outcome measures.
4. Time to start weight-bearing in a boot, in days.
5. Time to start weight-bearing in shoes, in days.

6. Time to return to full unrestricted activity, in days.
7. Change in pain at the base of the big toe (bunion related) assessed via a Visual Analog Scale (VAS) at 0-14 days, 14-21 days, 6 weeks, 4 months, 6 months, 12 months and 24 months post-Lapiplasty® Procedure, in comparison to baseline visit pain.
8. Change in Quality of Life, (PROMIS-29, PROMIS-25 and MOxFQ) defined as the total score measured at 6 months, 12 months and 24 months post-Lapiplasty® Procedure, in comparison to baseline visit.
9. Change in Range of Motion - 1st MTP dorsiflexion and plantarflexion at 12 months and 24 months post-Lapiplasty® Procedure, in comparison to baseline visit.
10. Change, if any, in initial incision length during Lapiplasty® Procedure.
11. Change in radiographic foot length and width at 12 months post-Lapiplasty® Procedure in comparison to baseline visit.
12. Change in swelling at 6 weeks and 4 months post-Lapiplasty® Procedure as compared to 0-2 week visit.
13. Change in scar quality at 4 months, 6 months, and 12 months post-Lapiplasty® Procedure in comparison to baseline visit.
14. Correlation between amount of time external positioner is actively used during Lapiplasty Procedure with necrosis, blistering, bruising and tissue ulceration events.

[figure not shown]

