## **Foot Measurements–**

### **Baseline and Pre-operatively**

Using a flexible tape measure, measure the circumference of the forefoot using the most prominent projection at the medial 1st metatarsal head and the lateral 5th metatarsal head as the starting reference points. Measure in a circumferential manner. Remove slack from the tape so that it lays flat on the skin.

Using a flexible tape measure, measure the circumference of the foot using the 1st TMT articulation as the starting reference point. Determine the position of the TMT via manipulation of the metatarsal through a dorsiflexion/plantarflexion movement. Palpation and visualization of the joint puckering through the soft tissue will allow for the approximation of this landmark. Mark the area with a surgical marking pen for reference. If this is unsuccessful in allowing the surgeon to determine the level, a metallic bb marker can be placed on the skin and plain film radiographic imaging can be utilized to approximate the anatomy. Determine the TMT position and measure in a circumferential manner. Remove slack from the tape so that it lays flat on the skin.

Using a flexible tape measure, measure the circumference of the ankle using the medial and lateral malleolus as reference points. Hold the measuring tape just superior to the inferior edge of the medial malleolus. Wrap the tape around the ankle, remove all slack and ensure the tape is flat on the lateral malleolus. The measurement should be made perpendicular to the longitudinal axis of the tibia and fibula.

Measure the circumference of the mid-calf at the tibia. Approximate the Myotendinous junction of the gastroc. Measure the distance from this landmark to the popliteal fossa. Determine the midline and measure in a circumferential manner. Remove slack from the tape so that it lays flat on the skin.

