### **Post-operatively**

Using a flexible tape measure, measure the circumference of the forefoot using the most prominent projection at the medial 1st metatarsal head and the lateral 5th metatarsal head as the starting reference points. Measure in a circumferential manner. Remove slack from the tape so that it lays flat on the skin.

Using a flexible tape measure, measure the circumference of the foot using the midpoint of the surgical incision as the starting reference point. Determine the midline and measure in a circumferential manner. Remove slack from the tape so that it lays flat on the skin.

Using a flexible tape measure, measure the circumference of the ankle using the medial and lateral malleolus as reference points. Hold the measuring tape just superior to the inferior edge of the medial malleolus. Wrap the tape around the ankle, remove all slack and ensure the tape is flat on the lateral malleolus. The measurement should be made perpendicular to the longitudinal axis of the tibia and fibula.

Measure the circumference of the mid-calf at the tibia. Approximate the Myotendinous junction of the gastroc. Measure the distance from this landmark to the popliteal fossa. Determine the midline and measure in a circumferential manner. Remove slack from the tape so that it lays flat on the skin.

**Range of Motion** – Dorsiflexion and plantarflexion should be measured while subject is passive and non-weightbearing with the study provided goniometer. To measure ROM, the arms of goniometer should be lined up parallel to longitudinal axis of the 1st metatarsal and proximal phalanx of the hallux with the axis at the center of rotation of the first metatarsal head.

**Radiographic Measurements** - Radiographic measurements will be analyzed by a third-party independent radiologist and entered into Clinindex. The radiographic measurements that will be collected, at a minimum, are provided in **Appendix 4**. Additional exploratory radiographic measurements may be collected without requiring a protocol amendment.

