6.1 Baseline

Baseline values are those which were collected at the Baseline visit (Visit 1). If a baseline value is missing, then the most recent value collected within 90 days prior to the Index Procedure will be used.

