7.2.2 Secondary Effectiveness Analysis

Effectiveness analyses will be performed on the following secondary endpoints:

- 1) Percentage of subjects with recurrence at 12 months where recurrence is defined as meeting 2 of the following 3 criteria: IMA of $\geq 12^\circ$, HVA $\geq 20^\circ$ and TSP ≥ 4 .

- 2) Percentage of subjects with recurrence at 12 months and 24 months where recurrence is defined as HVA >15°.
- 3) Percentage of subjects with recurrence at 12 months and 24 months where recurrence is defined as HVA >20°.
- 4) Percentage of subjects with successful correction at 6 weeks.
- 5) Change from baseline in radiographic angular/positional alignment for HVA, IMA, TSP, and sagittal plane at 6 weeks, 4 months, 6 months, 12 months, and 24 months.
- 6) Percentage of subjects with non-union (absence of clinical/radiographic healing) at 12 months.
- 7) Time to weight-bearing in a controlled ankle motion (CAM) boot, in days.
- 8) Time to weight-bearing in shoes, in weeks.
- 9) Time to return to full unrestricted activity, in months.
- 10) Change from baseline in pain at the base of the big toe (bunion related) assessed via VAS at 0-14 days, 14-21 days, 6 weeks, 4 months, 6 months, 12 months, and 24 months.
- 11) Change from baseline in Quality of Life at 6 months, 12 months, and 24 months as measured by PROMIS-29 (for adult subjects), PROMIS-25 (for pediatric subjects), and MOxFQ (for all subjects).
- 12) Change from baseline in range of motion of the 1st MTP dorsiflexion, plantarflexion, and dorsiflexion plus plantarflexion at 4 months, 6 months, 12 months, and 24 months.
- 13) Change from baseline in foot swelling measurements at 0-14 days, 14-21 days, 6 weeks, 4 months, 6 months, and 12 months.
- 14) Summary of POSAS responses over time at 4 months, 6 months, 12 months, and 24 months.

Statistical summaries will be produced in accordance with section 7, and listings will be generated by site, subject, and visit (where applicable) within subject.

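### Averaging the two pre-operative foot circumferences (Visits 1 and 2) would tighten the SAP's change-from-baseline swelling analysis, by at most a quarter of the variance and plausibly much less

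*Protocol*

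**What the plan says.** **Two pre-operative readings.** Protocol 7.1 includes foot measurements among the Visit 1 items, under the instruction "The following procedures must be conducted within 90 days prior to the index procedure". Protocol 7.2 lists "Foot Measurements" again at Visit 2, ahead of the index procedure. Both Schedules of Assessments mark the two visits. Section 7.12 describes one four-site method (forefoot, 1st TMT level, ankle, mid-calf) under the heading "Baseline and Pre-operatively".

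**Baseline rule.** SAP 6.1 states: "Baseline values are those which were collected at the Baseline visit (Visit 1". If that value is missing, the latest one from the 90 days before surgery replaces it. No averaging rule appears, and the SAP states no other use of the Visit 2 circumferences.

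**Swelling analyses.** SAP 7.2.2, item 13 plans "Change from baseline in foot swelling measurements at 0-14 days, 14-21 days, 6 weeks, 4 months, 6 months, and 12 months". Secondary endpoint 12 in protocol 3.0 is instead "Change in swelling at 6 weeks and 4 months post-Lapiplasty® Procedure as compared to 0-2 week visit". The synopsis and SAP 1.2.2 also use the early post-operative visit as the reference. SAP 6.4.2, which names the variables analysed as change from baseline, does not include foot circumference.

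**Midfoot landmark.** Before surgery the instruction is to "measure the circumference of the foot using the 1st TMT articulation as the starting reference point". After surgery it is to "measure the circumference of the foot using the midpoint of the surgical incision as the starting reference point".

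**The concern.** A second pre-operative reading by the same method is required of every treated subject, yet the SAP gives it no role when Visit 1 is present. Error in the single baseline reading passes in full into every change score under item 13. SAP section 7 tests change from baseline with two-sided t-tests at 0.05. Averaging two readings would reduce that error without new data, so the item 13 intervals are wider than they need be. At stake is precision in one descriptive secondary analysis, not bias or validity.

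**Working it through.** **Inputs.** The documents give no SD, reliability or correlation for foot circumference, and the sample size of 200 has no calculation behind it, so there is no planned figure to reproduce. The correlations below are assumptions.

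**Variance of change.** Let B1 and B2 be the Visit 1 and Visit 2 readings and Y a post-operative reading. Assume a common variance s², correlation ρ₀ between B1 and B2, and correlation ρ₁ between each of them and Y.

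- One baseline reading: Var(Y − B1) = 2s²(1 − ρ₁).
- Mean of two: Var(Y − (B1+B2)/2) = s²[1 + (1 + ρ₀)/2 − 2ρ₁].
- Difference: s²(1 − ρ₀)/2.
- Proportional reduction: (1 − ρ₀) / [4(1 − ρ₁)].

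If ρ₀ = ρ₁ the reduction is 1/4 whatever their common value. If ρ₀ exceeds ρ₁ it is smaller. With ρ₀ = 0.95:

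| ρ₁ | Reduction in variance | SE ratio |
|---|---|---|
| 0.95 | 0.05/0.20 = 25% | √0.75 = 0.866 |
| 0.90 | 0.05/0.40 = 12.5% | √0.875 = 0.935 |
| 0.80 | 0.05/0.80 = 6.3% | √0.9375 = 0.968 |
| 0.70 | 0.05/1.20 = 4.2% | √0.958 = 0.979 |

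**The same result as an error model.** Give each reading an independent error of variance s², and let true change vary between subjects with variance r·s². The two variances are (2 + r)s² and (1.5 + r)s², so the reduction is 0.5/(2 + r): 25% at r = 0, 16.7% at r = 1 and 8.3% at r = 4. A simulation of 400,000 subjects gave 25.1%, 16.8% and 8.4%. The 25% case therefore means that every subject has the same true change. If the two pre-operative errors correlate at 0.5, the reduction is 12.5% even at r = 0.

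**Effect on an interval.** With 200 evaluable subjects (assumed), the 95% half-width using Visit 1 alone is 1.96/√200 = 0.139 SD of change. Multiplying by the SE ratio gives 0.120 at a 25% reduction, 0.130 at 12.5% and 0.136 at 4.2%.

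**Endpoint 12.** The contrast is Y(6 weeks or 4 months) − Y(0-14 days). No pre-operative reading enters, so the reduction is 0%.

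**Midfoot.** If moving from the TMT joint to the incision midpoint shifts the reading by δ on average, then both Y − B1 and Y − (B1+B2)/2 contain δ. Averaging leaves it untouched.

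**The case against.** One pre-specified baseline with a fallback is a valid choice. The study is mainly descriptive and rests no decision on swelling. Subjects should be expected to differ in true change after surgery, most obviously at the forefoot, where the correction itself alters the contour being measured. That pushes ρ₁ below ρ₀ and the gain well below 25%. All of this stands: it limits the size of the point and makes it optional. It does not give the required Visit 2 reading a purpose, and the SAP's own fallback could already accept that reading as a baseline.

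A reader might infer more than the documents support:

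- **That the SAP discards Visit 2.** It does not; the value can serve when Visit 1 is missing.
- **That averaging cuts the variance by a quarter generally, as if there were a third more subjects (1/0.75 = 1.33).** That needs equal correlations, which nothing in the documents supports.
- **That every swelling interval is too wide.** Endpoint 12 uses no pre-operative value.
- **That the Visit 1-Visit 2 difference measures tape repeatability.** The readings may be up to 90 days apart, and rater, posture and time of day are not fixed, so it mixes tape error with other variation.
- **That day within the 0-14 day window should be a covariate.** The documents give no time course for swelling, and the planned analysis is a one-sample test of change. An adjustment would need a model, a functional form and a reference day.

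**Conclusion.** The point holds as an efficiency improvement to SAP 7.2.2, item 13, and not as an error. Averaging reduces the variance of change by up to 25%, and by about 4% to 12.5% for ρ₁ between 0.70 and 0.90 with ρ₀ = 0.95. The ceiling rests on equal variances, both pre-operative readings relating equally to the post-operative one, and a pre-pre correlation at least as high as the pre-post correlation. The gain is clearest at the ankle and calf, whose landmarks do not change; at the midfoot any systematic shift remains.

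The check also exposes a matter that averaging does not settle. Endpoint 12 and item 13 use different reference visits, and SAP 6.4.2 omits foot circumference although item 13 needs it.

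**What to change.** 1. In SAP 6.1, add: for foot circumferences, baseline is the mean of the Visit 1 and pre-operative Visit 2 values, or whichever one is available if the other is missing.
2. In SAP 6.4.2, add foot circumference to the change-from-baseline variables.
3. Reconcile the swelling reference visit between endpoint 12 (protocol 3.0 and synopsis; SAP 1.2.2) and SAP 7.2.2, item 13. If both contrasts are wanted, list both and say which one answers the endpoint.
4. Optionally, report the within-subject SD from the Visit 1-Visit 2 pair with Table 6, labelled as pre-operative test-retest variability (tape error plus natural, rater and setting variation).

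Items 1, 2 and 4 need SAP wording and a little programming. Item 3 may also need a protocol clarification if the endpoint itself is changed. No visit, measurement or subject burden is added.

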### **7.3 Visit 3 – 0-14 Day Follow-Up**

The following must be conducted:

- Digital photograph of operative foot, not required
- Clinical Exam of operative foot
- Foot Measurements
- Wound Assessment/healing of surgical site including damage by external positioner
- VAS Pain Scale
- Post Operative use of compression sock, if applicable
- Return to Weight-Bearing Activities (CAM boot fitting, if not on day of surgery)
- Secondary Surgical Interventions
- Medications Review
- Adverse Event Assessment
- Health Economic Outcomes

### **7.4 Visit 4 – 14-21 Day Follow-Up (+ 3 days)**

The following must be conducted:

- Digital photograph of operative foot, not required
- Clinical Exam of operative foot
- Foot Measurements
- Wound Assessment/healing of surgical site including damage by external positioner
- VAS Pain Scale
- Post Operative use of compression sock, if applicable
- Return to Weight-Bearing Activities (CAM boot fitting – if not at previous visit)
- Secondary Surgical Interventions
- Medications Review
- Adverse Event Assessment
- Health Economic Outcomes

### **7.5 Visit 5 – 6 Week Follow-Up ( $\pm$ 2 weeks)**

The following must be conducted:

- Digital photograph of operative foot, not required
- Radiographic Imaging (axial view may be missed if patient is unable to use positioning block due to post-operative range of motion limitations)
- Clinical Exam of operative foot
- Foot Measurements
- Wound assessment/healing of surgical site including damage by external positioner
- VAS Pain Scale
- Post Operative use of compression sock, if applicable

- Return to Weight-Bearing Activities
- Secondary Surgical Interventions
- Medications Review
- Adverse Event Assessment
- Health Economic Outcomes
- Radiographic Measurements

